10.4 Ocular Discomfort Scale

The  Ocular Discomfort Scale (ODS) will be collected at Screening (Visit 1) and Week 4 (Visit 4a; pre-CAE and post-CAE). Subjects will grade themselves on the ODS with scores from 0 to 4 to indicate the level of discomfort: 0 corresponds to “No discomfort”, 1 to “Intermittent awareness”, 2 to “Constant awareness”, 3 to “Intermittent discomfort”, and 4 to “Constant discomfort”. The ODS collected at Visit 4a will be used to determine treatment administration. Treatment of study drug will be administered when a participant reports an ODS ≥ 3 at two or more consecutive time points in at least one eye during CAE exposure (subjects with an ODS of 3 at time 0 for an eye must report an ODS of 4 for two consecutive measurements for that eye) using the Ora Calibra Scale. ODS will be summarized by visit, pre-CAE and every 5 minutes in CAE at Visit 4, and treatment group for both study and fellow eyes.

10.5 Ocular Surface Disease Index (OSDI)

The OSDI will be collected at screening. The protocol provides the questionnaire, calculation, and details of categorization. The OSDI score will be summarized by treatment

with quantitative descriptive statistics (n, mean, median, standard deviation, 25th quartile, 75th quartile, minimum, and maximum).

10.6 Corneal Fluorescein Staining

Corneal fluorescein staining will be performed and data will be collected at Screening (Visit 1), Week 4 (Visit 4b), and Early Termination (if necessary). Corneal fluorescein staining will be assessed for both the study and fellow eye. Staining will be graded using the National Eye Institute (NEI)/Industry Workshop Scale. Examiners will score each of five areas on the cornea of each eye: 1 – Central; 2 – Superior; 3 – Temporal; 4 – Nasal; 5 – Inferior. A standardized grading system of 0-3 will be used for each of the five areas. The corneal fluorescein staining score will be described by visit, treatment, study eye, and fellow eye with summary statistics. Specifically, scores will be presented by each of the five cornea areas and total scores for all corneal areas.

10.7 Slit Lamp Biomicroscopy

The slit lamp biomicroscopy will be performed at Screening (Visit 1, pre-and post-treatment procedures), Day 7 (Visit 2), Week 2 (Visit 3), Week 4 (Visit 4b, pre-and post-treatment procedures), Week 6 (Visit 5), Week 24 (Visit 6), Week 48 (Visit 7), and Early Termination (if necessary). A slit lamp will be used for external examination and biomicroscopy. The eyelids, cornea, conjunctiva, anterior chamber, iris, and lens will be examined at each visit. Slit lamp biomicroscopy results will be summarized for each treatment group for the study and fellow eye by visit using discrete summary statistics. Abnormal clinically significant findings will be described. Shifts from baseline including normal to abnormal (not clinically significant), and normal to abnormal (clinically significant) will be presented using counts and percentages

11 Intranasal Examination

Intranasal assessments collected at Screening (Visit 1), Day 7 (Visit 2), Week 4 (Visit 4b), and Early Termination (if necessary) will be summarized by treatment group with counts and percentages. Shifts from baseline of normal to abnormal (not clinically significant) and normal to abnormal (clinically significant) will be presented using counts and percentages.

[figure not shown]

12 Efficacy Analysis

Table 1. Hierarchical order of hypothesis testing

OC-01 Nasal Spray, 0.6 mg/mL vs. placebo	OC-01 Nasal Spray, 1.2 mg/mL vs. placebo
Primary endpoint	
[Redacted]	[Redacted]
Secondary endpoints	
[Redacted]	[Redacted]
[Redacted]	[Redacted]
[Redacted]	[Redacted]
[Redacted]	[Redacted]
.....
[Redacted]	[Redacted]

Footnote:

1.

[figure not shown]

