### 6.2 Safety Measures

- Adverse Events
- Intranasal Exam
- Slit Lamp Biomicroscopy

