### **Visit 2 (Day 7 ±2): Dosing Compliance Assessment**

- BCVA
- EDS (visual analog scale)
- Slit lamp biomicroscopy
- Intranasal exam
- Concomitant Medications
- AE Query

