**Visit 4b (Minimum +3 Days after Visit 4a)**

**Schirmer's Test Evaluation:**

- EDS (visual analog scale) (post treatment)
- BCVA (pre and post treatment)
- Slit lamp biomicroscopy (pre and post treatment)
- Corneal fluorescein staining (post treatment)
- Intranasal examination (pre and post treatment)
- Administration of study drug/placebo
- Schirmer's Test (concurrent with treatment)
- Concomitant medications
- AE Query

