**Visit 5 (Day 42  $\pm$  3): 6 Week Safety Assessment**

- Slit lamp biomicroscopy
- Intranasal examination
- Concomitant Medications
- AE Query

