#### 10.5.6 Safety Analysis

All safety analyses will be performed on the safety population.

The safety of OC-01 (varenicline) will be assessed primarily by the incidence of AEs. An AE will be considered a treatment-emergent AE (TEAE) if it occurs or worsens on or after initiation of treatment. An overall summary of TEAEs will be presented including the number of events and the number of subjects with events (along with percentages) by treatment group for TEAEs in several categories base on seriousness, relationship to treatment, and severity.

Other safety endpoints including visual acuity, slit-lamp biomicroscopy and intranasal examination will be summarized by treatment group and visit using descriptive statistics. Changes or shifts from baseline will be summarized where appropriate. For assessments performed by eye, study eye and fellow eye will be summarized separately.

The SAP will present methods of analysis of these defined parameters in detail.

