The objective of this study is to evaluate the safety and effectiveness of OC-01 (varenicline) Nasal Spray as compared to placebo on signs and symptoms of dry eye disease (DED).

5 Study Design

This is a Phase 3, multicenter, randomized, controlled, double-masked study designed to evaluate the safety and efficacy of OC-01 (varenicline) Nasal Spray in adult participants with DED. Approximately 750 subjects at least 22 years of age with a physician's diagnosis of dry eye disease and meeting all other study eligibility criteria will be randomized to receive an application of OC-01 (varenicline) Nasal Spray or placebo twice daily (BID) for 28 days with three additional long-term follow-up visits at 6 weeks, 6 months and 12 months.

The three treatments are:

- Placebo (vehicle) [control]
- OC-01 (varenicline) Nasal Spray, 0.6 mg/mL
- OC-01 (varenicline) Nasal Spray, 1.2 mg/mL

Subjects who terminate early during the study period will be asked to complete safety assessments (if the subjects agree) prior to study exit. Subjects who are terminated early from the study will not be replaced.

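### SAP section 11 leaves Visits 5, 6 and 7 out of the intranasal examination summary, although the exam is scheduled there and Protocol 10.5.6 promises a summary by visit

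*SAP*

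**What the plan says.** Protocol section 6.2 lists "Intranasal Exam" among three safety measures, with adverse events and slit lamp biomicroscopy. Protocol section 8.3.1 schedules the exam at Visit 1, Visit 2, Visit 4b and each of Visits 5, 6 and 7.

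Protocol section 10.5.6 states the planned analysis: "Other safety endpoints including visual acuity, slit-lamp biomicroscopy and intranasal examination will be summarized by treatment group and visit using descriptive statistics". It leaves the detail to the other document: "The SAP will present methods of analysis of these defined parameters in detail".

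SAP section 11 supplies that detail, as counts and percentages for each arm: "Intranasal assessments collected at Screening (Visit 1), Day 7 (Visit 2), Week 4 (Visit 4b), and Early Termination (if necessary) will be summarized". A second sentence promises shifts from baseline to abnormal, both clinically significant and not, and names no visits.

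The SAP knows of the follow-up. Its section 5 describes treatment for 28 days "with three additional long-term follow-up visits at 6 weeks, 6 months and 12 months". Its section 10.7, immediately before section 11, names Weeks 6, 24 and 48 (Visits 5, 6 and 7) for slit lamp and says those results are summarized by visit.

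Protocol section 10.5 and SAP section 3 both say that the SAP governs where the two documents disagree.

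**The concern.** A list that names visits defines what goes into the table. Read literally, SAP 11 tabulates the nasal exam at baseline, during treatment and at early termination, and nowhere in the planned follow-up. It also drops the protocol's wording that the summary is by visit.

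The stake is the description of nasal safety after dosing stops. Visits 5, 6 and 7 are titled safety assessments, and the only two clinical examinations scheduled at all three are slit lamp and intranasal. The plan assures a by-visit, by-arm summary for the eye and not for the nose, which is where the drug is applied.

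The question is a live one in the protocol's own account of the earlier study. Its synopsis says that drug-related adverse events resolved before that study ended, except those under three terms: nasal dryness, nasal congestion and throat irritation. Two of these are nasal.

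**Working it through.** No sample size, power or error-rate figure bears on this point. The check is a count of visits with the passages set side by side.

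**Inputs.** Scheduling is taken from the visit procedures in Protocol 8.3.1, because the rows of the Appendix 1 tables are broken in the available text. The summary lists are those in SAP 11 (intranasal) and SAP 10.7 (slit lamp). The early-termination column is left out, since both SAP sections name it.

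| Visit | Nominal day | Intranasal exam scheduled | Named in SAP 11 | Slit lamp scheduled | Named in SAP 10.7 |
|---|---|---|---|---|---|
| 1 (baseline) | 1 | yes | yes | yes | yes |
| 2 | 7 | yes | yes | yes | yes |
| 3 | 14 | no | – | yes | yes |
| 4b | 28 | yes | yes | yes | yes |
| 5 | 42 | yes | **no** | yes | yes |
| 6 | 168 | yes | **no** | yes | yes |
| 7 | 336 | yes | **no** | yes | yes |

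The relevant entries in Protocol 8.3.1 read "Intranasal exam" at Visit 2, "Intranasal examination (pre and post treatment") at Visit 4b, and "Intranasal examination" at Visits 5, 6 and 7.

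**Counts.**

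- Post-baseline visits with a scheduled intranasal exam: 2, 4b, 5, 6, 7 = 5.
- Of these, named in SAP 11: 2 and 4b = 2.
- Not named: 5 − 2 = 3.
- If Visit 1 is counted as well, 3 of 6 scheduled visits are not named.
- Across Visits 5 to 7, slit lamp is named at 3 of 3 and the intranasal exam at 0 of 3.

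The count is by visit and not by exam, because Visit 4b has one exam before dosing and one after.

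**Position of the omitted visits.** Relative to Day 28 they fall nominally at 42 − 28 = 14, 168 − 28 = 140 and 336 − 28 = 308 days. They are all of the scheduled exams after treatment, and the two visits that remain are both within the treatment period.

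**Could other text restore them?**

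- Protocol 10.5.6 would, but it hands the detail to the SAP, and the precedence clauses favour the SAP.
- SAP Appendix 1 is a schedule of what is collected. It does not say what is summarized.
- SAP 3 says the SAP rests on the original protocol, while the protocol supplied is Amendment 1. That does not explain the gap, because SAP 5 and the columns of SAP Appendix 1 already include the three follow-up visits.
- The shift sentence in SAP 11 may or may not reach Visits 5 to 7, since it names no visits.

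**The case against.** The strongest reply is that this is an omission and not a contradiction. SAP 11 does not say that only the named visits count, and nothing in it forbids a by-visit table. Protocol 10.5.6 can be read together with it: the protocol supplies by treatment group and visit, and the SAP adds counts, percentages and shifts. On that reading the precedence clauses are never triggered. The shift sentence has no visit limit, and for an exam graded normal or abnormal the shift table is the more informative output.

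The practical loss can also be called small. Every on-treatment visit with a scheduled exam is named. Adverse events are collected to the last follow-up visit (Protocol 9.1), and neither definition of a treatment-emergent event (Protocol 10.5.6, SAP 13.1) has an end date. Late nasal findings that qualify as adverse events would therefore appear in the non-ocular tables. Every result is listed by treatment and visit (SAP 9.1 and 13), and unresolved adverse events are followed (Protocol 9.5).

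Much of this stands, and it limits the weight of the point. It does not remove it. The combined reading is possible, but a programmer working from SAP 11 would build the table from its list. The safeguards are partial. Listings in a trial of about 750 subjects do not give counts and percentages by arm. An abnormal finding that is not clinically significant, which SAP 11 itself intends to tabulate, need not be recorded as an adverse event. Following unresolved events is subject management and not an analysis.

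**Conclusion.** The point holds. As written, SAP 11 is narrower than Protocol 10.5.6 and out of step with SAP 10.7. It omits 3 of the 5 post-baseline visits with a scheduled intranasal exam, and these are all of those after the treatment period. The claim is that by-arm tabulation at those visits is not assured. It is not a claim that the data are lost or that the tables could not be produced.

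Severity is low to moderate. Adverse events are the primary safety measure under Protocol 10.5.6, and no efficacy result or error rate is touched. It should still be corrected, because the exam is a named safety measure for a nasal product.

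The conclusion rests on two assumptions. The first is that the list in SAP 11 is followed as it reads. The second is that no blacked-out text elsewhere in the SAP supplies the missing table, which cannot be checked; the sentence in SAP 11 itself is complete and readable.

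**What to change.** In SAP section 11:

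1. Add Week 6 (Visit 5), Week 24 (Visit 6) and Week 48 (Visit 7) to the list of visits.
2. State that the summary is by visit and treatment group.
3. State that the shift summary covers the same post-baseline visits.

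This brings SAP 11 into line with Protocol 10.5.6 and SAP 10.7. The cost is about one sentence of SAP text and a few more rows in a table already planned. The exams are already scheduled, so no new data are needed.

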**5.4 Exclusion Criteria**

**Subjects must not:**

[REDACTED]

- 6. Have had any intraocular surgery (such as cataract surgery) or extraocular surgery in either eye within three months or refractive surgery (e.g. laser-assisted in-situ keratomileusis, laser epithelial keratomileusis, photorefractive keratectomy or corneal implant) within twelve months of Visit 1

[REDACTED]

- 12. Have a history or presence of any ocular disorder or condition in either eye that would, in the opinion of the Investigator, likely interfere with the interpretation of the study results or participant safety such as significant corneal or conjunctival scarring; pterygium or nodular pinguecula; current ocular infection, conjunctivitis, or inflammation not associated with dry eye; anterior (epithelial) basement membrane corneal dystrophy or other clinically significant corneal dystrophy or degeneration; ocular herpetic infection; evidence of keratoconus; etc. Blepharitis not requiring treatment and mild meibomian gland disease that are typically associated with DED are allowed.

- 14. Have a systemic condition or disease not stabilized or judged by the Investigator to be incompatible with participation in the study or with the lengthier assessments required by the study (e.g., current systemic infection, uncontrolled autoimmune disease, uncontrolled immunodeficiency disease, history of myocardial infarction or heart disease, etc.)

- 15. Have a known hypersensitivity to any of the procedural agents or study drug

OC-01 (varenicline) Nasal Spray  
Clinical Trial Protocol # OPP-101  
Amendment #1

Sponsor: Oyster Point Pharma, Inc.

components

- 16. [REDACTED]

18. Have any condition or history that, in the opinion of the investigator, may interfere with study compliance, outcome measures, safety parameters, and/or the general medical condition of the subject

[REDACTED]

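### SAP 11 limits intranasal shift summaries to shifts from normal, so worsening from not clinically significant to clinically significant is not tabulated; SAP 10.7 leaves the same slit-lamp shift unnamed

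*SAP*

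**What the plan says.** SAP 11 (Intranasal Examination) says of the shift summaries: "Shifts from baseline of normal to abnormal (not clinically significant) and normal to abnormal (clinically significant) will be presented using counts and percentages". No word in that sentence opens the list to other shifts. The only other intranasal output in SAP 11 is that assessments "will be summarized by treatment group with counts and percentages".

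SAP 10.7 (Slit Lamp Biomicroscopy) says: "Shifts from baseline including normal to abnormal (not clinically significant), and normal to abnormal (clinically significant) will be presented using counts and percentages". The word *including* makes these two shifts examples. The section adds that "Slit lamp biomicroscopy results will be summarized for each treatment group for the study and fellow eye by visit using discrete summary statistics", and that "Abnormal clinically significant findings will be described". On what is examined: "The eyelids, cornea, conjunctiva, anterior chamber, iris, and lens will be examined at each visit".

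Protocol 5.4, exclusion criterion 12, says: "Blepharitis not requiring treatment and mild meibomian gland disease that are typically associated with DED are allowed".

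Protocol 10.5.6 provides more generally for changes or shifts from baseline where appropriate, with no restriction to a normal baseline. Protocol 10.5 and SAP 3 both give the SAP precedence where the two differ. Protocol 6.2 lists three safety measures: adverse events, the intranasal exam and slit lamp biomicroscopy.

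**The concern.** A shift table shows, subject by subject and by arm, who got worse on a graded examination. Both SAP sections use three grades: normal (N), abnormal not clinically significant (NCS) and abnormal clinically significant (CS). If every tabulated shift starts from N, a subject who starts at NCS can never be counted as worse.

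This matters most for the nose. The product is sprayed into each nostril twice daily for 28 days (Protocol 5.1 and 7.1.1). The protocol's risk summary reports that nasal dryness, nasal congestion and throat irritation were the exceptions to suspected-related events having resolved before ONSET-1 ended. For the eye, the population may bring lid findings to baseline, so NCS to CS is a plausible route of worsening there too. What is at stake is the completeness of the planned tables for two of the three listed safety measures. No efficacy conclusion is involved.

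**Working it through.** No figure in the plan is in dispute, so there is none to reproduce. The check compares the wording of the sections and then considers size.

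**1. Which worsening shifts are named.** With three ordered grades there are three possible worsening cells.

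| Baseline | To N | To NCS | To CS |
|---|---|---|---|
| N | unchanged | named | named |
| NCS | improved | unchanged | **not named** |
| CS | improved | improved | unchanged |

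Two of the three worsening cells are named in each section; NCS to CS is named in neither.

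**2. Exclusion or silence.** In SAP 11 the two shifts are the stated content of the table, so a programmer following the text would produce those two and no others. Protocol 10.5.6 is broader, but the SAP prevails. In SAP 10.7 the list is open: NCS to CS may be added or left out, and either choice complies with the plan.

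**3. Whether other outputs supply the missing cell.** Let a be the number moving N to CS, b NCS to CS, and c CS to CS. Among subjects with both assessments, the follow-up CS count is a + b + c, so

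b = (follow-up CS count) − a − c.

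The named shift gives a. The by-visit counts give the follow-up and baseline CS totals, provided they are split by clinical significance. Only c is unknown, and it lies between 0 and the baseline CS count. If nobody is CS at baseline, c = 0 and b can be recovered. Otherwise only bounds are available: if 20 subjects move NCS to CS and 20 move CS to NCS, the net change in the CS count is 20 − 20 = 0.

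For the eye, the opening text of SAP 10 says that grade and clinical significance will be tabulated. That text covers ocular assessments. SAP 11 is a separate section and does not say that its counts are split by clinical significance, so recovery is less assured for the nose.

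**4. Size.** Inputs: about 250 subjects per arm (Protocol 10.4, SAP 7), and b₀, the share of noses abnormal at baseline. The documents do not give b₀; the range below is an assumption. Subjects per arm who cannot contribute to a shift that starts from normal = 250 × b₀.

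| Assumed b₀ | Subjects per arm outside the named shifts |
|---|---|
| 10% | 25 |
| 25% | 62.5, about 63 |
| 50% | 125 |
| 75% | 187.5, about 188 |
| 90% | 225 |

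The choice of denominator also matters. If 10% truly worsened to CS whatever their baseline grade (a second assumption), a table with all subjects as denominator would show 0.10 × (1 − b₀): 8%, 5% and 2% at b₀ = 0.2, 0.5 and 0.8. This shows the mechanism only and is not an estimate. Under the same assumption, with b₀ similar across randomized arms, the difference between arms shrinks by the factor 1 − b₀ but the risk ratio is expected to be unchanged. The formula does not carry over to slit-lamp results by structure, because an eye with an abnormal lid can still shift on the cornea or conjunctiva.

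**The case against.** The strongest reply is that little is lost. A pre-existing condition that worsens after dosing is a new adverse event (Protocol 9.1), and a TEAE includes an event that has worsened in severity (SAP 13.1). Clinically significant slit-lamp findings are described whatever the baseline grade. All safety parameters are listed by subject and visit (SAP 13). Corneal staining is graded separately from 0 to 3 in five areas of each eye (SAP 10.6). All of this stands, and it rules out any claim that worsening goes unreported. None of these outputs gives within-subject worsening on the graded exam by arm. Adverse event tables depend on the change being reported as an event, and listings do not compare arms.

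A reader might infer three stronger things that the documents do not support.

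- *That both sections count only shifts from normal.* This is true of SAP 11. It is not true of SAP 10.7, whose list is open.
- *That the blepharitis and meibomian allowance shows the intranasal restriction to be harmful.* That text concerns eyes. Nothing readable describes the nose at baseline, and several exclusion criteria are redacted. The case for the nose rests on its being the site of administration.
- *That many enrolled eyes are already abnormal.* Such findings are allowed, but no frequency is given, and Protocol Appendix 2 does not say they must be graded abnormal.

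**Conclusion.** The point holds as a minor matter of safety reporting. SAP 11 restricts intranasal shifts to those starting from normal, so NCS to CS is not tabulated for the exam of the site of administration. In SAP 10.7 the same shift is unnamed rather than excluded, while abnormal lids at baseline are foreseeable.

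The size cannot be fixed, because it depends on a baseline share that the documents do not give. If almost no noses are abnormal at Visit 1, the gap is negligible; if half are, about 125 subjects per arm lie outside the intranasal shift table. The conclusion rests on reading the SAP 11 sentence as a complete list, which its contrast with the wording of SAP 10.7 supports. Alpha, power, sample size and the efficacy analyses are unaffected.

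**What to change.** In SAP 11, and for consistency in SAP 10.7, replace the named shifts with a full 3x3 baseline-by-visit table (N, NCS, CS) for each arm. For the slit lamp, present it by structure and by eye.

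Add one summary line to each: the number and percentage worsening by one or more categories from baseline. The denominator is the number at risk, meaning those graded N or NCS at baseline and assessed at that visit.

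The cost is a change of SAP wording and a slightly larger safety table. The shifts already named require all three grades, so no new data are needed.
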